### **C. SUBJECTS TO BE INCLUDED**

**Describe:** The inclusion criteria for the study population includes: an interest in taking NEP lessons, willingness to wait 1 year to start NEP lessons, eligibility for SNAP, age of at least 18 years, not pregnant, living in a household located in Indiana, ability speak and read English, willingness to complete three 30 minute surveys at the designated time intervals, willingness to provide height and weight measurements, willingness to complete one 30 minute dietary recall and 60 minute FFQ at each assessment time point, willingness to stay in touch with NEP educators, and no previous participation in NEP lessons within the last year.

The exclusion criteria only include not meeting the inclusion criteria.

Women who are pregnant will not be able to enroll in the study; however, once recruited, participants who become pregnant during the study period will be able to continue participating in the study.

The study population may be considered vulnerable because they are a low income and low resource population that may have a lower than average level of education. Precautions will be taken to minimize potential risks to the study population.

The maximum number of participants targeted for the study is  $n=800$ ,  $n=400$  in the control group and  $n=400$  in the experimental group. Previous studies were used to calculate these estimates. Based on these “short term” studies, a 7% rate of attrition ( $n=17$  out of 236) is expected to increase to approximately 40% ( $n\approx 320$  of 800) in the proposed study due to the duration of 1 year between the post-assessment and the follow-up assessment. Based on these attrition considerations and our previous work, a sample size of  $n=800$  will be the recruitment goal (control group  $n=400$  and intervention group  $n=400$ ) with an approximate final sample size of  $n=480$  expected.

NEP educators will make no more than four coordinated efforts to remind participants of their participation in the study during the one year period between the second assessment and the final assessment. These attempts will also serve to update contact information, which NEP educators normally collect as part of their normal programming. Purdue researchers do not have access to participant names or home addresses. Purdue researchers only have participant names on consent forms and these documents are separated and stored separately from surveys. There is no way for researchers to identify participants or match their surveys with names. All participants in the study are also clients of the NEP Educators because they currently participate in the Nutrition Education Program as a participant in the intervention study group, or will participate at the conclusion of the study because they have indicated that they have the desire to participate as part of eligibility for the research study. The methods for contacting the participants include phone calls from the NEP educators, emails, physical flyers mailed to participants' home addresses, and a raffle. The email and physically mailed flyer will use the same content (attached). NEP educators will either email or physically mail the flyer, not both, depending on which method is preferred by the participant. All contact methods will be the same for control and intervention study group participants and are described below. Researchers will not directly contact participants unless the participant has requested telephone assistance to complete the dietary recalls and FFQ. Participants who have not completed the dietary recalls and FFQ in the amount of time provided will be called and asked if they would like to complete the dietary recalls and FFQ at that time over the phone, if they would like for researchers to resend the email link, or if they would like to make an appointment for researchers to call at a later time to complete the dietary recalls and FFQ over the phone. Participants will also be provided a Purdue telephone number for contacting researchers to complete the dietary recalls and FFQ.

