## APPLICATION TO USE HUMAN RESEARCH SUBJECTS

---

9. This project will be conducted at the following location(s): (please indicate city & state)
- Purdue West Lafayette Campus
- Purdue Regional Campus (Specify): \_\_\_\_\_
- Other (Specify): Indiana Nutrition Education Program class locations throughout Indiana, these may include: Emergency food distribution centers; Supplemental Nutrition Assistance Program (SNAP) offices; Women, Infant, and Children Program (WIC) offices; participant homes
10. If this project will involve potentially vulnerable subject populations, please check all that apply.
- Minors under age 18
- Pregnant Women
- Fetus/fetal tissue
- [Prisoners Or Incarcerated Individuals](#)
- University Students (PSYC Dept. subject pool \_\_\_\_)
- Elderly Persons
- Economically/Educationally Disadvantaged Persons
- Mentally/Emotionally/Developmentally Disabled Persons
- Minority Groups and/or Non-English Speakers
- Intervention(s) that include medical or psychological treatment
11. Indicate the anticipated maximum number of subjects to be enrolled in this protocol as justified by the hypothesis and study procedures: 800 (400 for control group and 400 for experimental group)
12. This project involves the use of an **Investigational New Drug (IND)** or an **Approved Drug For An Unapproved Use**.
- YES       NO
- Drug name, IND number and company: \_\_\_\_\_
13. This project involves the use of an **Investigational Medical Device** or an **Approved Medical Device For An Unapproved Use**.
- YES       NO
- Device name, IDE number and company: \_\_\_\_\_
14. The project involves the use of [Radiation or Radioisotopes](#):
- YES       NO
15. Does this project call for: (check-mark all that apply to this study)
- Use of Voice, Video, Digital, or Image Recordings?
- Subject Compensation? Please indicate the maximum payment amount to subjects. \$100  
[Purdue's Human Subjects Payment Policy](#)      [Participant Payment Disclosure Form](#)
- VO2 Max Exercise?
- More Than Minimal Risk?
- Waiver of Informed Consent?
- Extra Costs To Subjects?
- The Use of Blood?      Total Amount of Blood \_\_\_\_\_  
Over Time Period (days) \_\_\_\_\_
- The Use of [rDNA or Biohazardous materials](#)?
- The Use of Human Tissue or Cell Lines?
- The Use of Other Fluids that Could Mask the Presence of Blood (Including Urine and Feces)?
- The Use of Protected Health Information (Obtained from Healthcare Practitioners or Institutions)?
- The Use of academic records?

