### B. SPECIFIC PROCEDURES TO BE FOLLOWED

NEP educators are considered key personnel because they will have direct contact with study participants; however, they will not have any part in data entry, analysis, or dissemination of study results. NEP educators, employees of Purdue University Extension, across Indiana will help facilitate the study. NEP educators have completed CITI training as a requirement for employment through Purdue University Extension. Before recruiting study participants, participating NEP educators will attend training sessions facilitated by the co-investigators of the study. The training sessions will include instructions on how to interact with participants; answer questions related to the study; and protocol for administering surveys, measuring height and weight, keeping participant information private, and the use of identification numbers. The study goals and hypothesis will not be shared with the NEP educators in order to keep their work with the participants as unbiased as possible.

NEP educators will recruit study participants who are interested in participating in NEP. The details of recruitment are described in Section D. A screening survey determining eligibility will be administered in addition to an explanation of consent. After completion of the screening survey and consent process, NEP educators will randomize participants into one of two groups: control or experimental. The NEP educators will be assigned a random number using Excel and then listed in order from least to greatest according to their random number. The first half of the NEP educators will assign their first recruited participants to the experimental group. After the first assignment, they will alternate assigning participants to either study group in an "every other" participant fashion. The second half of the NEP educators will assign their first recruited participants to the control group. After the first assignment, they will also alternate assigning participants to either study group in an "every other" participant fashion. The control group will wait 1 year from taking the second survey before starting NEP lessons. The experimental group will start NEP lessons immediately. Participants in the experimental group must take at least the first 4 NEP lessons within a time period of 4 to 10 weeks. The NEP SNAP-Ed curriculum includes 10 lessons, and participants may take the additional 6 lessons if desired.

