## SNAP-Ed Sequel Statistical Analysis Plan

**Methods:** Up to 2 repeated online 24 hour dietary recalls using the Automated Self-Assisted 24-hour Recall (ASA-24) and the Diet History Questionnaire II (DHQ II) (web-based food frequency questionnaire) developed and provided by the National Cancer Institute will be used to estimate dietary intake; the Estimated Average Requirements (EAR) for nutrients (or Adequate Intake(AI) for nutrients that do not have an EAR) will be used as a dietary reference; the Healthy Eating Index-2010 will be used to characterize diet quality using data collected from the ASA-24; the 18-item US Household Food Security Survey Module (USHFSSM) will be used to assess household food security; the Nutrition Education Program (NEP) Medium Term Survey and additional questions will be used to assess participant characteristics, nutrition and health knowledge, and nutrition and health behavior

**Characteristics:** Study participant characteristics at baseline will be compared across the intervention and control groups to test for potential confounders to test for in regression models. Characteristics of participants who withdrew from the study will also be compared to those who completed the study.

**Diet Quality:** The Healthy Eating Index-2010 scoring algorithm will be used to characterize diet quality. Instructions and sample SAS code are provided by the National Cancer Institute website at <https://epi.grants.cancer.gov/hei/>. The simple algorithm will be used in order to assign HEI scores to each individual to be able to match and compare individual participants over time using regression modeling. Change in diet quality in the intervention group compared to the control group over time is one primary outcome.

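### Enrolment is not limited to one adult per household, and alternation puts household members recruited consecutively by the same educator in opposite arms, removing the food security contrast for such pairs and diluting the diet contrast

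*Protocol*

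**What the plan says.** Protocol Section C requires each participant to be "living in a household located in Indiana". That criterion sets where the household is, not how many of its adults may join. The section then closes the list: "The exclusion criteria only include not meeting the inclusion criteria".

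Protocol Section B has individual educators make the allocation. Half of them start with the experimental arm and half with the control arm, and from then on "they will alternate assigning participants to either study group" participant by participant. The comparison depends on controls going without the lessons: "The control group will wait 1 year from taking the second survey before starting NEP lessons".

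The SAP Methods paragraph says the 18-item module "will be used to assess household food security". The Food Security paragraph plans a mixed regression model for change in food security, names no household term, and lists the score as a possible covariate or secondary outcome. Protocol Section A nevertheless includes food security in both the study goal and the hypothesis. Under Diet Quality, the SAP scores the Healthy Eating Index for each person and makes its change a primary outcome.

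**The concern.** The lessons cover nutrition and food resource management (Protocol Section A), which can be expected to affect how a household buys and prepares food. If one adult takes the lessons and another adult in the same home is a control, the control is exposed to what the trial is testing. On food security the two also report on the same household. Independent 1:1 randomisation would split such a pair half the time; alternation splits consecutive recruits every time.

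The error runs towards finding no effect, in a study whose results are meant to inform programme and policy decisions. It would also be hard to see afterwards. Section C says the researchers hold no home addresses, and no household identifier is described. Educators do hold addresses (Section D), but nothing asks them to flag shared households, and Section F has them destroy the code key when the study ends.

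**Working it through.** **The plan's own figure.** Section C expects about 40% attrition from 800: 0.40 × 800 = 320 lost and 800 − 320 = 480 left. The short-term rate is 17/236 = 7.2%, stated as 7%. Both reproduce. No alpha, power, effect size or standard deviation is given, so there is no power calculation to reproduce.

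**Allocation.** Under strict alternation, recruits k and k + 1 of one educator differ in arm with probability 1, whichever arm came first. With exactly one other recruit between them they share an arm. If different educators recruit them, either result is possible.

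**Effect on food security.** Let f be the share of participants in split pairs; it is an assumption, because the documents give no value. Each pair puts one member in each arm, so a share f of each arm is affected. Both members report the same household outcome, so their contrast is 0, apart from differences in reporting and survey timing. With true effect Δ:

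expected difference = (1 − f) × Δ + f × 0 = (1 − f) × Δ.

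**Effective number of completers.** Information is proportional to effect² / variance.

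- Pairing ignored: the variance is taken as for 480 independent people, so the factor is (1 − f)².
- Pairing respected: a pair with identical outcomes adds nothing to the variance of the difference in arm means, which becomes (1 − f) times its usual value. The factor is (1 − f)² / (1 − f) = 1 − f.

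| f | Recruits in split pairs (of 800) | Effect kept | Ignored: 480 × (1 − f)² | Respected: 480 × (1 − f) |
|---|---|---|---|---|
| 2% | 16 | 98% | 461 | 470 |
| 5% | 40 | 95% | 433 | 456 |
| 10% | 80 | 90% | 389 | 432 |

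Respecting the pairing corrects the standard error but not the estimate, which is still multiplied by (1 − f).

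**Power, for scale.** Assume two-sided alpha of 5% and an effect that gives 80% power with 240 completers per arm: (1.960 + 0.842) × √(2/240) = 0.256 SD. With pairing ignored, power is about Φ(2.802 × (1 − f) − 1.960) = 78.4%, 75.9% and 71.3% at f = 2%, 5% and 10%. With pairing respected it is Φ(2.802 × √(1 − f) − 1.960) = 79.2%, 78.0% and 75.7%.

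**Diet outcomes.** Let w be the share of the contrast lost within a split pair, unknown between 0 and 1. The effect is multiplied by (1 − f × w). With w = 0.5 as an illustration, f = 5% keeps 97.5% and f = 10% keeps 95%.

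**One adult per household.** If the second adults are not replaced, the trial loses f/2 of its completers: 480 × (1 − f/2) = 475, 468 and 456, with power 79.6%, 79.0% and 78.0%. At each f this exceeds both columns above, and the estimate is not diluted. With replacement up to 480, power stays at 80%.

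**The case against.** The strongest objection is that such pairs may be rare. Each adult must personally want the lessons, accept a possible one-year wait, and agree to surveys, weighing, recalls and a food frequency questionnaire at three time points. No passage supports 10%, which would mean 80 of 800 recruits. This stands: at 2% the loss is small. On the other side, each participant can earn up to $100 (Section E), so a second adult has some reason to join, and a cheap safeguard does not need f to be large.

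The screening survey is listed as an attachment in Section M but not shown, so it may already ask about other household members. That also stands, although Section C's closed list gives no ground for excluding anyone on the answer.

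A reader might infer more than the documents support:

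- *That the trial's effect is cancelled.* Cancellation applies only to household food security within split pairs. The primary diet outcomes are individual, and only dilution of unknown size can be argued for them.
- *That any two household members are split.* This is certain only for consecutive recruits of the same educator.
- *That participants are recruited at home.* Item 9 of the application does list "participant homes", but among class locations; it does not call them recruiting sites.
- *That ignoring the pairs inflates false positives.* For positively correlated members in opposite arms the reverse holds: the standard error is too large, which is conservative.

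**Conclusion.** The point holds as a gap in eligibility that the allocation rule makes worse. The listed criteria admit several adults per household, consecutive recruits of one educator are always split, and no household identifier or model term is planned. For a split pair the food security contrast is essentially zero; the diet contrast is weakened by an amount the documents cannot settle.

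The overall size depends on f, which is unknown: the food security effect keeps 98% to 90% of its value over the assumed range of 2% to 10%. The lower set of effective sample sizes (461, 433, 389) applies only if the analysis ignores pairing; the higher set (470, 456, 432) applies if it does not. Both assume that the two members of a pair report identical household outcomes. Food security is at most secondary in the SAP, although it is part of the stated study goal. Severity is low to moderate.

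**What to change.** Add to the inclusion criteria in Protocol Section C, and to the screening survey, that no other member of the person's household is enrolled in the study. This costs one screening question and a few lost recruits, who can be replaced within the target of 800.

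Assigning a later household member to the first member's arm is not a good substitute. That person's arm would be known before consent, and the analysis would need a household identifier that the plan does not collect.

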**Flyer:**

- Flyers will include these components: thanking the participants for their participation, reminding them to update contact information with their NEP educator, information on an appropriate and free local event not related to nutrition or budgeting information in which the participants could take part, raffle information.
- NEP educators will either email the attached flyers to participants or physically mail the attached flyer to the participants' addresses they have on file.

**Phone Call:**

- NEP educators will call participants and update contact information, and either set an appointment to take the final survey or remind them of their appointment if already set

**Raffle:**

- Participants who complete the final survey before January 1st, 2017 will be entered into a \$500 raffle. The odds of winning are approximately 1 in 480 and one \$500 check will be awarded. The odds of winning may be updated on the study reminder flyer to reflect actual number of participants. The winner

will be randomly chosen by April 1st, 2017. If researchers are unable to contact the winning participant through their NEP Assistant after 3 attempts within one week (phone call, mailing, email), another participant will be randomly chosen. The winning participant may decline the \$500. The winning participant's name, address, and social security number or taxpayer identification number will need to be shared with researchers at Purdue only if they win the raffle and only for dispersing the \$500 check. The participant will also need to complete the Institutional Review Board Human Subject Receipt Log, which will be provided by the researchers. Non-resident alien recipients will have to complete information within the Glacier Tax Compliance software system ([www.online-tax.net](http://www.online-tax.net)) to assess tax reporting and withholding requirements. This is explained in the consent form. Other than previously stated, no payment or additional action is required to enter the raffle. Participation in additional research or other consideration is not necessary. Void where prohibited or restricted by law. Subject to all federal, state, and local laws.

- The raffle will be advertised on the scheduled email and physically mailed flyers and through phone calls to participants.

**Proposed Retention Tasks Timeline:**

Month	Retention Task
January	
 
• Email Flyer/ Mail physical flyer to home address
 

March	
 
• Phone Call
 

May	
 
• Email Flyer/ Mail physical flyer to home address
 

July	
 
• Phone Call
 

**D. RECRUITMENT OF SUBJECTS AND OBTAINING INFORMED CONSENT**

NEP educators will recruit potential clients for the study. NEP educators will administer a screening survey to determine eligibility for the study. If potential participants do not wish to participate in the study or complete the screening survey, they may proceed with taking NEP lessons as usual without any effect on their relationship with the NEP, NEP educator, Extension, state or federal programs, or Purdue University. Study participants and non-participants may receive NEP lessons together without any effect on the study.

If a NEP client is eligible and willing to participate in the study, an informed consent form requiring their name and signature will be provided unless the IRB approves a waiver of signed consent, in which case NEP educators will explain the informed consent form to participants and allow them to read the consent form. If the consent form is provided electronically online, participants will be asked to select the “I agree” radio button to provide informed consent before proceeding to complete the survey. Participants will be provided their choice of an email or physical copy of the informed consent form.

NEP educators will facilitate data collection and use identification numbers to keep participant data together. NEP educators also collect private identifying information such as names, home addresses, email addresses, and telephone numbers for the NEP, but not as part of the study. The study investigators and co-investigators will receive the data with the participant identification numbers only and without any private identifying information. Researchers will be provided with only participant phone numbers and email addresses which will be linked only to participant identification numbers and never linked with participant names.

**E. PROCEDURES FOR PAYMENT OF SUBJECTS**

Study participants will be paid either in cash or through gift certificate to compensate them for the time they have spent in the study. NEP educators will provide participants \$5 in cash for completing the first survey in person and a \$10 gift certificate for completing the in person portions of surveys 2 and 3. Participants will receive a gift certificate of \$15 for completing both the first dietary recall and FFQ and a \$10 gift certificate for completing the second dietary recall at all 3 assessment time points. Participants may receive up to \$30 for the first assessment and up to \$35 for the second and third assessments. The gift certificate will be chosen by the participant from participating stores through an online gift certificate company and emailed to participants or mailed to participants' homes by the NEP educator, depending on the participant's preference. Participants could receive up to a monetary value of \$100 for completing all three surveys.

